#### **10.7.9 Sample Size Determination**

The sample size for this study was based upon the results of the previous Phase 2 study, TR-H-211. In that study, Merlin demonstrated a statistically significant ( $p=0.0276$ ) effect on the duration of classical lesion endpoint for subjects beginning treatment at Stage 1 (erythema) with only 32 subjects treated with Merlin and 22 placebo subjects. Clinical investigations with Famvir and other independent studies, that initiate treatment within hours of the onset of prodromal symptoms (Stage 0) have demonstrated that 1/3 of all subjects enrolled in herpes labialis studies will have spontaneously aborted lesion. Any calculation of clinical trial size, therefore, must consider that factor. When, however, treatment is initiated at the erythema stage (Stage 1), as in the Merlin Phase 2a (TR-H-211) study, the incidence of spontaneously aborted lesions declines to 25%. As a result, a larger percentage of subjects will demonstrate classical lesions in Merlin studies than was seen in the Famvir, or similar previous studies. This was factored in when performing

power calculations for this Phase 2b clinical study. Those calculations determined that 144 subjects would provide a 95% likelihood of statistical significance for the herpetic episode endpoint. Merlin decreased the duration of herpetic episode in subjects that began treatment at stage 1 by 41 hours, with a p-value of 0.055 in the Phase 2a study. The herpetic episode endpoint includes the subjects with aborted lesions.

As a result, a 150 subject clinical trial will have approximately 60 subjects progress to classical lesions in each treatment arm and we can be highly confident of having the power to demonstrate a highly significant difference for the duration of classical lesion endpoint, as shown in the Phase 2a results. In addition, a 150 subject clinical trial should have greater than 95% likelihood of demonstrating a statistically significant Merlin effect on herpetic episode as a secondary endpoint.

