
Statistical Methods: Generally, statistical hypothesis tests will be two-tailed, and statistical significance will be declared when the p-value is less than 0.05. Continuous variables will be summarized using descriptive statistics, specifically the mean, median, standard deviation, minimum and maximum. Categorical variables will be summarized by frequencies and percentages.
 
All subjects who received (at least some) treatment, whether they were formally entered into the Treatment Phase of the study or applied the test material without formal authorization, will be included in the Safety Population. The safety analysis will be performed on the Safety Population.
 
All subjects who have been entered into the Treatment Phase of the study will be included in the Modified Intent to Treat (MITT) population. The MITT population will be used as the primary analysis population. All subjects who have been entered into the Treatment Phase of the study and have been followed successfully until their lesion healed, or until 14 days, whichever is earlier, will be included in the Efficacy Evaluable population. The efficacy analysis will be performed on both the MITT and the Efficacy Evaluable populations.
 
No imputation of missing data will be performed for the efficacy analyses for the Efficacy Evaluable population.
 
The duration of the classical herpetic lesion (both clinician and patient assessed) will be analyzed using the Hodges-Lehmann method as the primary efficacy analysis method for estimating the median difference between the two arms. Duration of the herpetic episode (both clinician and patient assessed), duration of complete healing of the herpetic episode (both clinician and patient assessed), duration of the herpetic lesion (both clinician and patient assessed), duration of the herpetic lesion hard scab (both clinician and patient assessed), and duration of pain will be analyzed in the same manner as the duration of the classical lesion.
 
The proportions of subjects in each treatment group who do not display classical lesions (prevention of progression to classical lesions) will be compared using Fisher's Exact Test.
 
For pain, the maximum severity will be analyzed using the Cochran-Mantel-Haenszel Test to test for differences between treatment groups.
		

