## **10.4 General Methodology**

All statistical tests will be done using two-sided tests and a Type I error rate of 0.05.

Data listings will be based on all subjects in the safety population.

Continuous variables will be summarized using descriptive statistics, specifically the mean, median, standard deviation, minimum and maximum values. Categorical variables will be summarized by frequencies and percentages.

The primary analyses will compare the active treatment arm to the placebo control arm. Aside from any placebo effect, there should be no efficacy associated with the placebo solution. As a secondary analysis, all statistical comparisons will be performed with the treated subjects stratified based on whether they treated at erythema (Stage 1) or papule/edema (Stage 2).

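### The 95% power stated for the herpetic episode is not supported by the printed Phase 2a figures at two-sided 0.05; if the printed 32/22 is the episode sample, they give about 90%

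*Protocol*

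**What the plan says.** Protocol 10.7.9 bases the sample size on TR-H-211. For the herpetic episode it states: "Those calculations determined that 144 subjects would provide a 95% likelihood of statistical significance for the herpetic episode endpoint". It adds that a trial of 150 "should have greater than 95% likelihood of demonstrating a statistically significant Merlin effect on herpetic episode as a secondary endpoint". SAP 3 makes the same two claims.

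The Phase 2a result behind them is given as: "Merlin decreased the duration of herpetic episode in subjects that began treatment at stage 1 by 41 hours, with a p-value of 0.055". Group sizes appear only once, in the sentence on the classical-lesion endpoint among Stage 1 starters: "with only 32 subjects treated with Merlin and 22 placebo subjects".

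The significance rule is set elsewhere. The synopsis (Statistical Methods) says that, in general, "statistical hypothesis tests will be two-tailed, and statistical significance will be declared when the p-value is less than 0.05". Protocol 10.4 says: "All statistical tests will be done using two-sided tests and a Type I error rate of 0.05", and SAP 7.2 repeats this. Protocol 10.7 and SAP 7.13.1 plan the Wilcoxon rank sum test with Hodges-Lehmann estimation for duration endpoints.

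The sample-size text does not give the test, SD, sidedness or episode group sizes used for the power calculation.

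**The concern.** A Phase 2a result that just missed 0.05 in 54 subjects fixes an approximate standardised effect. Scaling that effect to 144 or 150 subjects takes a few lines, and at two-sided 0.05 the result falls short of 95%.

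This matters because 95% is the only numerical power in either document; no figure is given for the primary endpoint. On the printed inputs, the chance of missing the assumed episode effect is about 10%, twice the 5% implied. The stake is limited, since the endpoint is secondary and neither the primary analysis nor enrolment depends on the figure.

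**Working it through.** **Inputs.** From Protocol 10.7.9: a 41 h difference, p=0.055, and 32 and 22 subjects. From Protocol 4: 1:1 allocation, so 72+72 at 144 and 75+75 at 150. From Protocol 10.4 and SAP 7.2: two-sided 0.05. Aborted lesions count in the episode endpoint, so N is not reduced for them.

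**Assumptions.** (a) 32/22 is also the episode sample. (b) p=0.055 is two-sided. (c) The Phase 2a test was about as efficient as the planned Wilcoxon test.

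**Step 1: standardised effect.** The effective size is 32 × 22 / 54 = 13.04, with square root 3.611.
- Normal: z for two-sided 0.055 is 1.919, so d = 1.919 / 3.611 = 0.531 and SD = 41 / 0.531 = 77 h.
- t with 52 df: 1.963, so d = 1.963 / 3.611 = 0.544 and SD = 41 / 0.544 = 75 h.

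**Step 2: power at two-sided 0.05.** The noncentrality is d × √(N/4). Normal power is Φ(noncentrality − 1.96); the t version uses the noncentral t with N − 2 df.

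| N | Noncentrality (z; t) | Normal | Noncentral t | Stated |
|---|---|---|---|---|
| 144 | 3.19; 3.26 | 89.0% | 90.0% | 95% |
| 150 | 3.25; 3.33 | 90.2% | 91.1% | over 95% |

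A simulated Wilcoxon test (normal data, d = 0.544, 20,000 runs) gives 88.4% and 89.7%. Rounding in p (0.0545 to 0.0555) moves power by about 0.1 point. Power of 95% at two-sided 0.05 would need about 178 (t) to 186 (normal, equal arms) subjects in total.

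**Step 3: other readings of the Phase 2a inputs, two-sided 0.05.**
- 32/22 are classical lesions only. With the stated 25% aborted rate, the episode sample would be 54 / 0.75 = 72, a number that is not printed. Power is then about 79-80% at 144 and 80-82% at 150.
- p=0.055 was one-sided: about 76% at 144.
- 144 is per arm: over 99%, which fits neither 95% nor a trial of 150 in total.

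**Step 4: what comes near the stated figures.**
- One-sided 0.05 with the Step 1 inputs: Φ(3.19 − 1.645) = 93.9% (normal) or 94.5% (t) at 144, and 94.6% or 95.2% at 150.
- A smaller SD: 95% at 144 needs 41 × √36 / (1.960 + 1.645) = 68 h.
- A mean-based Phase 2a p-value, followed by the Wilcoxon test on right-skewed data with a pure 41 h shift. Simulated gamma data with SD 75-77 h (shapes are assumed) give about 94-95% at 144 and about 95% at 150 for shape 3, and 96-97% at 144 for shape 2.

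**The case against.** The strongest reply is that the sponsor held the TR-H-211 data and a reader does not. The SD of 75-77 h is inferred from a p-value whose test is not named and from group sizes printed for another endpoint. An SD about 10% smaller would give 95% at 144. Lesion durations are positive and probably right-skewed, and under a shift effect the Wilcoxon test can beat a mean-based test by enough to close the gap.

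This stands as far as it goes: 95% at two-sided 0.05 is attainable. But the skewness route needs p=0.055 to come from a mean-based test. If Phase 2a also used the Wilcoxon test, skewed data still give about 89-90%; if treatment scales durations instead of shifting them, simulated power is about 85-88%. Doubt about the group sizes does not help either, since the classical-only reading lies further from 95%.

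The imprecision of the input is also a fair point. The 41 h has a standard error of about 41 / 1.919 = 21 h, so a shortfall of 4 to 6 points is small beside it. That limits the importance of the discrepancy but does not supply a basis for 95%.

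A reader might infer that the calculation was one-sided, because that nearly matches both figures. The documents do not support this: every statement on sidedness says two-sided, and two other routes fit about as well. A reader might also set the expected number of classical lesions per arm against the 25% aborted rate. That comparison shows no error: the rate is given for Stage 1 starters, this trial also admits Stage 2, each arm has at least 75 subjects, and the count is given as approximate.

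**Conclusion.** The concern holds as a minor one. The printed Phase 2a figures do not support the stated episode power at the planned two-sided 0.05. Under assumptions (a) to (c), power is about 89-90% at 144 and 90-91% at 150, against 95% and over 95%. If 32/22 counts classical lesions only, it is about 79-82%.

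A reader might go further and call the 95% an arithmetic error. The documents do not allow that: the inputs to the calculation are not printed, and at least three unstated choices would bring it close to the stated figures. The primary endpoint and its analysis are not affected.

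**What to change.** In Protocol 10.7.9 and SAP 3:

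1. Recompute the herpetic episode power from the TR-H-211 data for the planned two-sided 0.05 Wilcoxon test, at 144 and 150 subjects.
2. State the SD or assumed distribution, the test, the sidedness and the episode group sizes used.
3. Restate both power figures unless that calculation confirms them. On the printed figures the result would be about 90%, but the data should decide. If the calculation proves to have been one-sided, reconcile it with Protocol 10.4 and SAP 7.2.

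The cost is one recalculation from existing data and a revised sentence or two in each document. The stated power may become less favourable. Enrolment, conduct and the primary analysis stay as they are.

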## **11 ADMINISTRATIVE REQUIREMENTS**

### **11.1 Good Clinical Practice**

The study will be conducted in accordance with the International Conference on Harmonization (ICH) for Good Clinical Practice (GCP) and the appropriate regulatory requirement(s). Essential clinical documents will be maintained to demonstrate the validity of the study and the integrity of the data collected. Master Files should be established at the beginning of the study, maintained for the duration of the trial and retained according to the appropriate regulations.

### **11.2 Ethical Considerations**

The study will be conducted in accordance with ethical principles founded in the Declaration of Helsinki. The Institutional Review Board (IRB)/Independent Ethics Committee (IEC) will review all appropriate study documentation in order to safeguard the rights, safety and well-being of the subjects. The study will only be conducted when IRB/IEC approval has been obtained. The protocol, Investigator Brochure, informed consent, recruitment advertisements (if applicable), written information given to the subjects, safety updates, annual progress reports, and any revisions to these documents will be provided to the IRB/IEC by the Investigator.

### **11.3 Subject Information and Informed Consent**

After the study has been fully explained, written informed consent will be obtained from either the subject or his/her guardian or legal representative prior to study participation. The method of obtaining and documenting the informed consent and the contents of the consent will comply with GCPs and all applicable regulatory requirement(s).

## **11.4 Subject Confidentiality**

In order to maintain subject privacy, all CRFs, study clinical trial material accountability records, study reports and communications will identify the subject only by initials and the assigned study-specific Randomization Number. The Investigator will grant monitor(s) and auditor(s) from Topical Remedy, LLC, or its designee and regulatory authority(ies) access to the subject's original medical records for verification of data gathered on the CRFs and to audit the data collection process. The Sponsor, or designee of the Sponsor, also may observe the study in progress. The subject's confidentiality, per HIPAA regulations, will be maintained except as required by the applicable laws and regulations.

## **11.5 Protocol Compliance**

The Investigator will conduct the trial in compliance with the protocol provided by Topical Remedy, LLC, and given approval/favorable opinion by the IRB/IEC and the appropriate regulatory authority(ies). Modifications to the protocol should not be made without written agreement of both the Investigator and Topical Remedy, LLC. Changes to the protocol will require written IRB/IEC approval/favorable opinion prior to implementation, except when the modification is needed to eliminate an immediate hazard(s) to subjects. The IRB/IEC may provide, if applicable regulatory authority(ies) permit, expedited review and approval/favorable opinion for minor change(s) in ongoing trials that have the approval/favorable opinion of the IRB/IEC. Topical Remedy, LLC will submit all protocol modifications to the regulatory authority(ies) in accordance with the governing regulations.

When immediate deviation from the protocol is required to eliminate an immediate hazard(s) to subjects, the Investigator will contact Topical Remedy, LLC, if circumstances permit, to discuss the planned course of action. Any departures from the protocol must be approved by Topical Remedy, LLC and fully documented in the CRF and source documentation.

## **11.6 Study Monitoring**

Monitoring and auditing procedures developed by Topical Remedy, LLC, or its designee, will be followed, in order to comply with GCP guidelines. On-site checking of the CRFs for completeness and clarity, cross-checking with source documents, and clarification of administrative matters will be performed.

The study will be monitored by Topical Remedy, LLC, or its designee. Monitoring will be done by personal visits from a representative of the sponsor (site monitor) who will review the CRFs and source documents. The site monitor will verify that the investigation is conducted according to protocol design and regulatory requirements and will document their findings in frequent communications (email, letter, telephone, and fax).

All unused study materials that have not already been returned during the course of the clinical study, as per instructions from Topical Remedy, LLC, are to be returned to Topical Remedy, LLC, or their designee, after the clinical phase of the trial has been completed.

### **11.7 On-site Audits**

Regulatory authorities, the IEC/IRB, and/or Topical Remedy, LLC.'s Vice President of Clinical Research, or designee may request access to all source documents, CRFs, and other study documentation for on-site audit or inspection. Direct access to these documents must be guaranteed by the Investigator, who must provide support for these activities.

### **11.8 Case Report Form Completion and Data Management**

Topical Remedy, LLC, or its designee, will provide the study sites with a CRF for each subject. A subject screening log will be used to document any reason for screen failure. For each subject who has given informed consent, meets the study enrollment eligibility criteria, and is randomized into the trial, a CRF will be completed. The Principal Investigator will certify that the subjects were seen and evaluated by qualified site staff and that he/she has delegated responsibilities for subject evaluation as identified in the Study Site Roles and Responsibilities Log maintained in the study master file.

As appropriate, all source documents or CRF pages should be filled out during (or immediately after) a subject assessment. The text should be written with a black or blue ballpoint pen and must be legible. If a source document or CRF entry needs correction, the error should be crossed out with a single line (not obliterated or covered with correction fluid) and the correct information should be written next to the original entry. The change must be initialed and dated by the Investigator or designee.

The study monitor at the study site will review source documents, CRFs and any queries will be highlighted to the Investigator or designee enabling the errors to be addressed prior to collection of the CRF pages. Errors detected by subsequent in-house CRF review may necessitate clarification or correction.

Documentation of all data management activities should allow step-by-step retrospective assessment of data quality and study performance. This includes maintenance of documentation to support any changes or corrections applied to the CRFs.

Data collected on the CRFs will be entered into Topical Remedy, LLC designee's database by a dual entry system. The database will be checked for internal consistency, and the critical data will be compared with the original CRFs.

Queries arising during data processing/consistency checking will either be provided to the site for clarification and approval by the Investigator, or handled by the designee's Data Managers.

## **11.9 Clinical Trial Material Accountability**

Accountability for the clinical trial materials at the trial site is the responsibility of the Investigator. The Investigator will ensure that the clinical trial materials are used only in accordance with this protocol. Where allowed, the Investigator may choose to assign some of the clinical trial material accountability responsibilities to a pharmacist or other appropriate individual. Clinical trial material accountability records indicating the clinical trial material delivery date to the site, inventory at the site, use by each subject, return of used or unused clinical trial material by the subject to the site, and return to Topical Remedy, LLC (or disposal of the drug, if approved by Topical Remedy, LLC) will be maintained by the clinical site. These records will adequately document that the subjects were provided the clinical trial materials as specified in the protocol and should reconcile all study clinical trial materials received from Topical Remedy, LLC. Accountability records will include dates, quantities, and Randomization Numbers. The sponsor or its designee will review clinical trial material accountability at the site on an ongoing basis during monitoring visits. Accountability records must be current and up to date.

All unused and used study clinical trial materials will be retained at the site until they are inventoried by the monitor. All unused study drug will be returned to Topical Remedy, LLC, or if authorized, disposed of at the study site and documented.

## **11.10 Premature Closure of the Study**

This study may be prematurely terminated, if in the opinion of the FDA or Topical Remedy, LLC, there is sufficient reasonable cause. Written notification documenting the reason for study termination will be provided to the Investigator by Topical Remedy, LLC.

Circumstances that may warrant termination include, but are not limited to:

- Determination of unexpected, significant, or unacceptable risk to subjects
- Failure to enter subjects at an acceptable rate
- Insufficient adherence to protocol requirements
- Insufficient complete and/or evaluable data
- Plans to modify, suspend or discontinue the development of Merlin

Should the study be closed prematurely, all study materials (completed, partially completed, and blank CRFs, study clinical trial materials, etc.) must be returned to Topical Remedy, LLC.

## **11.11 Record Retention**

The Investigator will maintain all study records according to ICH-GCP and applicable regulatory requirement(s). Records will be retained for at least two years after the last marketing application approval or two years after formal discontinuation of the clinical development of the investigational product or according to applicable regulatory

requirement(s). The Sponsor will notify the Investigator when these time periods have elapsed. If the Investigator withdraws from the responsibility of keeping the study records, custody must be transferred to a person willing to accept the responsibility. Topical Remedy, LLC must be notified in writing if a custodial change occurs.

## 11.12 Liability and Insurance

Topical Remedy, LLC has subscribed to an insurance policy covering, in its terms and provisions, its legal liability for injuries caused to participating persons and arising out of this research performed strictly in accordance with the scientific protocol as well as with applicable law and professional standards.

## 12 USE OF INFORMATION

All information regarding the Merlin solution supplied by Topical Remedy, LLC to the Investigator is privileged and confidential information. The Investigator agrees to use this information to accomplish the study and will not use it for other purposes without consent from Topical Remedy, LLC. Any manuscript, abstract, or other publication or presentation of results or information arising in connection with the study must be prepared in conjunction with Topical Remedy, LLC. It is understood that there is an obligation to provide Topical Remedy, LLC with complete data obtained during the study. The information obtained from the clinical trial will be used towards the development of the Merlin solution and may be disclosed to regulatory authority(ies), other Investigators, corporate partners, or consultants as required.

